The goals of the Aim 3 pilot MRT are to (1) evaluate feasibility and acceptability of MRT methods and messages, and (2) collect proof-of-concept data on the comparative impact of maternal-focused and drinking-focused messages on proximal (motivation, self-efficacy, and self-regulation) and distal (alcohol use) outcomes. An MRT design is recommended for optimizing text messaging interventions because it provides an empirical basis for decisions about delivery of intervention components¹. In an MRT, participants are re-randomized at each decision point, allowing for the examination of causal time-varying effects of intervention components on proximal outcomes with a smaller number of participants, thus maximizing efficiency². The proposed study will pilot the MRT design to test the TMI for postpartum HED. Results will include feasibility and acceptability and preliminary main effects estimates to inform a fully-powered MRT in a future study.

Sample and Power

MRT participants will include 50 postpartum women who meet study eligibility criteria recruited following procedures described above (see Participants and Recruitment). In line with published recommendations for

Stage I intervention development research^{3,4,5} the primary goal of the pilot MRT is to assess feasibility and to generate provisional evidence of efficacy to inform planning a fully powered MRT, which will be conducted in a future study. Thus, our sample size of 50 was selected to balance recruitment feasibility with the goal of obtaining sufficient data to generate provisional evidence of main effects of intervention components⁵, and is consistent with other studies using MRT in the early stages of intervention development⁶. Given the small sample, we will interpret results based on effect size rather than statistical significance. Stage I studies are not required to demonstrate adequate power to detect significant effects³; thus, a formal power analysis was not conducted.

Procedures

Study participants will be recruited via social media, as described above (Participants and Recruitment). After signing informed consent, participants will proceed through the following steps.

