Step 1: Baseline Assessment. Participants who sign informed consent will be asked to complete a Baseline Assessment via Qualtrics. Participants will be sent a secure link to the Qualtrics survey via text or email. The Baseline will take approximately 30 minutes to complete and will include questions about demographics, parenting, mental health, stress and coping, motivation, and drinking and other substance use.

[figure not shown]
Step 2: Catalyst Training. Following completion of the Baseline, participants will participate in a one-on-one 15-minute training session with the RA via Zoom to provide training on how to download and use the Catalyst app. In order to avoid fraudulent participants, participants will be asked to turn on their camera for 1 minute of the training, after which they will be allowed to turn off their cameras for the remainder of the training if that makes them more comfortable. Participants who complete both the baseline survey and the Catalyst training session will receive a \$25 Amazon gift card upon completion of the Catalyst training session.

Step 3: 28-day MRT. After completing the training, the TMI sequence of EMAs and TMI text messages will begin as described below and will last for 28 days.

TMI Sequence and Randomization

Upon completion of the Catalyst training, the TMI sequence of EMAs and TMI component delivery will begin (see Figure 2).

Figure 2. TMI Sequence

There will be two decision points per day. Decision points will be randomly selected within a 12 hour window starting at the participant's pre-selected start time. There will be at least 4 hours between the two decision points. At each decision point, participants will receive the "decision point EMA." Upon completion of the decision point EMA, participants will be randomized to one of three options: (1) a maternal-focused message (.40 probability); (2) a drinking-focused message (.40 probability); or (3) no message (.20 probability). Fifteen minutes after randomization, participants will receive the "proximal outcome EMA." This sequence will repeat 2 times per day, at each decision point. Participants will also be sent a "morning survey" each morning within 30 minutes of their selected start time that will ask questions about the prior day. After each survey prompt, the survey will be

available for up to 60 minutes, with 2 reminder prompts sent (every 20 minutes). Surveys that are not completed within the 60 minute window will expire.

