Discrimination	
1. At any time yesterday did you feel that you were treated unfairly? (yes/no)
 
2. What was the main reason(s) for the unfair treatment that you experienced yesterday? (check all that apply)
 
 a. Your age b. Your gender c. Your race d. Your ethnicity or nationality e. Your religion f. Your height or weight g. Some other aspect of your appearance h. A physical disability i. Your sexual orientation j. Your drinking k. Your smoking l. Your other substance use m. Being poor n. Being a mother o. Other 
i. For "What was the main reason(s) for the unfair treatment that you experienced yesterday?" you selected other. Please write your response below:
 
3. Who treated you unfairly yesterday? (check all that apply)
 
 a. Family member b. Partner c. Stranger d. Acquaintance e. Employer f. Health care provider g. Other social service provider h. Other _____ 
i. For "Who treated you unfairly yesterday?" you selected other. Please write in your response below:

Decision Point/Daily EMA

[sent 2x daily]

Construct	Items
	
1. Were you with your baby since the last survey you completed? Yes/no [IF NO: Skip Baby Fussiness]
 
2. Will you be with your baby in the next hour? Yes/no [IF NO: Skip Maternal SE]

Maternal SE	How confident are you that you will be able to meet your baby's needs (such as needs to be fed, changed, soothed, or entertained) over the next hour? [Not at all confident to extremely confident 1-7]
Drinking SE ³³	How confident are you that you can avoid drinking for the next hour? [1 = not at all confident to 7 = extremely confident]
Stress ³⁴	Rate your overall stress level right now 1-7, very low to very high.
Mood	
1. What is your overall feeling right now [very unpleasant to very pleasant 1-7]
 
2. What is your overall energy level right now [very low to very high 1-7]
 
3. What is your anxiety level right now [very low to very high 1-7]

Fatigue ¹⁶	
1. How physically exhausted are you right now?
 
2. How mentally exhausted are you right now?
 
[not at all to extremely 1 -7]

Baby Fussiness ³⁵	
1. Since your last assessment, how many times did your baby fuss, cry, or seem upset? [0, 1, 2, 3, 4, 5, 6, 7, 8, 9, 10 or more times]
 
2. How many of these times were you able to successfully soothe your baby? [all of them, most of them, some of them, a few of them, none of them]

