Intent to Drink ³³	How committed are you to not drink in the next hour? [1 = not at all to 7 = extremely]
Urge to Drink	How strong is your urge to drink right now? 1= very low, 7=very high

Drinking	4. Did you consume any alcohol in the past hour? Yes/no 5. If yes, how many drinks did you consume?
----------	--

Proximal Outcome EMA

Construct	Items
Maternal SE	How confident are you that you will be able to meet your baby's needs (such as needs to be fed, changed, soothed, or entertained) over the next hour? [Not at all confident to extremely confident 1-7]
Drinking SE ³³	How confident are you that you can avoid drinking for the next hour? [1 = not at all confident to 7 = extremely confident]
Intent to Drink ³³	How committed are you to not drink in the next hour? [1 = not at all to 7 = extremely]
Urge to Drink	How strong is your urge to drink right now? 1= very low, 7=very high
Drinking	6. Did you consume any alcohol since the last survey you received? Yes/no 7. If yes, how many drinks did you consume?
Stress coping	1. Since the last survey you completed, did you use any strategies to cope with negative feelings or stress? a. I didn't experience negative feelings or stress since the last survey b. I drank alcohol c. I changed my thinking d. I changed my current situation to cope with negative feelings or stress e. I found something else to do f. I sought advice or support g. I came up with a plan to cope with negative feelings or stress h. I set a goal or kept track of my progress towards my goal i. I directly communicated my needs to others j. I tried to relax k. I took medication l. I pushed negative feelings or stress away m. I used another strategy n. I didn't use any strategies to cope with negative feelings or stress 2. In the previous question you indicated that you took medication to cope with negative feelings or stress. Was this medication intended for the purpose of managing negative feelings or stress/for the purpose of managing alcohol cravings? a. Yes b. No 3. Was this medication prescribed to you by your healthcare provider? a. Yes b. no 8. You selected "I used another strategy to cope with stress". Please describe what you did below:

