Given that this is a pilot MRT and not powered to detect statistically significant effects, our primary focus in interpretation of findings is to assess feasibility of this design for a future fully-powered optimization trial. Feasibility analysis will include: (1) Recruitment Feasibility: We will evaluate length of time to recruit 50 MRT participants and demographic and clinical characteristics of those who enroll vs. those who decline enrollment; (2) Engagement Feasibility: We will examine paradata collected automatically by the TMI platform, including number of EMAs responded to, number of messages viewed, and number of days of engagement; (3) Retention Feasibility: We will track retention rates and predictors of retention using logistic regression analyses. We will follow the general recommendations of Klasnja and colleagues for analysis of MRT data to inform JITAI³⁶ optimization. Multilevel mixed effects models will be the primary analytic approach, and will account for nesting of observations within participant³⁷. To test main effects of TMI components on the proximal outcomes, we will first examine models that include only the intercept and a term for the TMI component. The coefficient associated with TMI component represents the mean difference in proximal outcome between person times when the component is delivered and person times when it is not delivered, averaged across the study period. We will compute the standardized effect size for all main effects following the recommendations of Luers et al¹.

PARTICIPANT INCENTIVES

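### The only main-effect model written out has no covariates; adding the same item's pre-randomization value would sharpen four proximal outcomes modestly at no data cost

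*Combined protocol and SAP*

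**What the plan says.** The MRT Data Analysis section plans multilevel models with observations nested in women. The one main-effect model it describes is "we will first examine models that include only the intercept and a term for the TMI component". Its coefficient is read as the mean difference between "person times when the component is delivered and person times when it is not delivered". The section also points to published general recommendations for MRT analysis and to a published method for standardizing effects. It names no covariate and writes out no later model.

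TMI Sequence and Randomization gives the order of events: "Upon completion of the decision point EMA, participants will be randomized to one of three options". The options are a maternal-focused message (0.40), a drinking-focused message (0.40) or none (0.20). The proximal outcome EMA follows 15 minutes later. It can be missed: "Surveys that are not completed within the 60 minute window will expire".

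The Decision Point/Daily EMA and Proximal Outcome EMA tables share four items word for word: Maternal SE, Drinking SE ("How confident are you that you can avoid drinking for the next hour"), Intent to Drink ("How committed are you to not drink in the next hour") and Urge to Drink. Maternal SE has a skip rule before randomization: "Will you be with your baby in the next hour? Yes/no [IF NO: Skip Maternal SE". The proximal table shows no such skip. The drinking item changes its look-back period between the two tables, and the coping items have no earlier version.

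Under Sample and Power, no power analysis was done, and "we will interpret results based on effect size rather than statistical significance".

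**The concern.** In this design every randomized point comes with a fresh measurement taken just before randomization. For four outcomes that measurement is the same question. A nested model already removes stable differences between women. It does not remove the moment-to-moment variation within a woman, part of which the earlier answer predicts. A model without that answer leaves the variation in the residual.

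The plan reads these effects by their size and will use them to inform a fully powered MRT, so the width of the intervals around them matters. If an adjusted model is wanted later, it is better fixed now than chosen after the results are seen.

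The contrast also has to be settled before any standard error can be quoted. With three options, a message type being not delivered could mean no message, or no message together with the other message type. That ambiguity would stand without any argument about adjustment and adds no weight to it.

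**Working it through.** The plan states no standard error, SD or power, so there is no figure to reproduce.

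**Inputs from the documents.** 50 women; 2 decision points per day for 28 days, so 56 per woman (the optional nighttime sequence is not counted); allocation 0.40/0.40/0.20.

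**Assumptions (not in the documents).** 60% of scheduled points yield an outcome; ICC 0.5, so the within-woman variance is 0.5 in units of the total outcome variance; r = 0.3, 0.5 or 0.7.

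**Step 1: points.** 50 × 56 × 0.60 = 1680, of which 672 maternal, 672 drinking and 336 none.

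**Step 2: same effect in every woman.** Unadjusted SE = sqrt(0.5 × (1/n1 + 1/n2)). Adjustment replaces 0.5 by 0.5 × (1 − r²), so the SE is multiplied by sqrt(1 − r²) for any contrast: 0.954, 0.866 and 0.714, cuts of 5%, 13% and 29%.

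| Contrast | n1, n2 | Unadjusted SE | Adjusted, r = 0.3 / 0.5 / 0.7 |
|---|---|---|---|
| One type vs none | 672, 336 | 0.047 | 0.045 / 0.041 / 0.034 |
| Maternal vs drinking | 672, 672 | 0.039 | 0.037 / 0.033 / 0.028 |
| One type vs everything else | 672, 1008 | 0.035 | 0.034 / 0.031 / 0.025 |

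At 50% response the unadjusted SEs are 0.052, 0.042 and 0.039; at 80%, 0.041, 0.033 and 0.031. The percentage cuts do not change.

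Simulation with 50 women, 56 points, 70% completion and some carry-over between points (600 runs per setting) gave cuts of 4.4%, 13.1% and 28.2% on a continuous scale. On a 1–7 scale with a ceiling they were 3.2%, 9.8% and 21.3%, r being the correlation before rounding. Mean estimates with and without adjustment agreed within 0.002, as expected with constant randomization probabilities.

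**Step 3: effects that vary between women** (SD 0.2, independent for the two types, assumed). This adds a variance that adjustment cannot touch: 0.04/50 = 0.0008 for one type versus none, and 0.08/50 = 0.0016 for maternal versus drinking.
- One type versus none: 0.055 falls to 0.053 / 0.050 / 0.044, cuts of 3%, 10% and 20%.
- Maternal versus drinking: 0.056 falls to 0.054 / 0.052 / 0.049, cuts of 2%, 6% and 13%.

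**Step 4: ratings at the scale end.** In a simulation of 1500 runs (50 women × 34 points, ICC 0.5, correlation before rounding 0.3/0.5/0.7), the cut was about 2%, 9% and 18% with 70% of ratings at the end of the scale, and about 2%, 6% and 14% with 90% there.

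**Step 5: both together (approximate).** Apply the step 4 cut c to the within-woman term only, with h the added variance from step 3: ratio = sqrt((V(1 − c)² + h)/(V + h)).
- One type versus none, V = 0.00223, h = 0.0008. At r = 0.5, c = 0.09 gives sqrt(0.00265/0.00303) = 0.935, a cut of 6.5%; c = 0.06 gives 4.4%.
- Maternal versus drinking, V = 0.00149, h = 0.0016. At r = 0.5 the cuts are 4.2% and 2.8%.
- At r = 0.3 (c = 0.02) they are 1.5% and 1.0%.

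**Step 6: the Maternal SE skip.** With skip share s (not in the documents) and r = 0.5, a missing indicator multiplies the SE by sqrt(1 − (1 − s)r²): a cut of 11% at s = 20% and 9% at s = 30%. Dropping the skipped points multiplies it by sqrt((1 − r²)/(1 − s)): 3% lower at s = 20%, 3.5% higher at s = 30%. The indicator is the better rule.

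**Step 7: completion.** In a simulation of 1500 runs (true effect 0, r = 0.5, about 80% completion), both models averaged 0.00 when completion was unrelated to the message. When completion after a message fell as the outcome rose (log-odds −0.5 per within-woman SD, assumed), the averages were −0.069 unadjusted and −0.052 adjusted, in outcome SD units. Adjustment did not remove the bias.

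**The case against.** The strongest reply is that little hangs on this. Feasibility is the primary goal, no power is claimed, no go/no-go threshold uses these effects, and the unadjusted model is legitimate. That stands, and it is why the point is minor.

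The plan also cites outside recommendations for the analysis and for standardizing effects, and its wording announces a first model, not the only one. That stands too. A reader might infer that the plan rules out adjustment or discards the pre-values. The text supports only that no adjusted model is specified. Whether the cited sources cover it cannot be judged from the documents.

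The 5%/13%/29% figures are a best case. Steps 3 to 5 show how far they shrink. Piling at the scale end is plausible, because eligibility rests on the T-ACE or on drinking before pregnancy, not on current drinking. With varying effects alone and r = 0.5, the 95% half-width for maternal versus drinking moves only from 0.109 to 0.102 SD (1.96 × 0.0556 and 1.96 × 0.0521).

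Two limits of scope also stand. Maternal SE is not asked before every randomization, and other items may be blank, since the plan itself counts completion by measure. And a covariate need not match the outcome's wording. The past-hour drinking item is measured before randomization, so it could properly be used for the proximal drinking outcome.

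None of this removes the point: a more precise model is available from data already collected, and it is not pre-specified.

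**Conclusion.** The point holds as a minor, free improvement. The planned estimate is less precise than it could be for four proximal items. For each of them the SE reduction is at most 5%, 13% or 29% at r = 0.3, 0.5 or 0.7. If effects vary between women and ratings also pile up, the cut at r = 0.5 is roughly 3% to 7%. At r = 0.3 it is negligible throughout. These sizes rest on assumed values of r, response, ICC, effect variation and rating distribution, none of which the documents give.

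A reader might go further and infer that the planned estimate is biased. The documents do not support that: randomization probabilities are constant and the pre-value precedes randomization, so the unadjusted contrast is valid if proximal EMA completion does not depend on the message. If that condition fails, both models can be biased, and adjustment is not a cure.

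**What to change.** Keep the unadjusted model as the first step and add to MRT Data Analysis:

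1. For Maternal SE, Drinking SE, Intent to Drink and Urge to Drink, a second main-effect model that adds the same item's value from the same decision point EMA.
2. Named contrasts: each message type versus no message, and maternal versus drinking.
3. Participant-clustered robust standard errors, with both models reported on one common standardizer consistent with the effect-size method already cited.
4. For any skipped or blank pre-value, a constant plus a missing indicator, so that adjustment loses no randomized point that has an outcome.
5. Optionally, the past-hour drinking item as a covariate for the proximal drinking outcome.
6. Proximal EMA completion shown by randomized option, because both models depend on it.

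The cost is a few sentences in the SAP and a little more analysis work. No new data are needed. Points whose proximal EMA expired are lost under either model.

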
The study has three primary aims:

Aim 1: Test and refine the proposed theoretical model via Ecological Momentary Assessment (EMA). This aim will refine the theoretical model underlying the TMI that specifies the impact of the proposed intervention components on the theoretical risk factors for postpartum RD, as well as decision rules for adaptive tailoring. Aim 1 work will include cellphone-based data collection using EMA with 30 women for 14 days to determine patterns and fluctuations of stress, negative mood, and self-efficacy in response to perceived sleep quality and baby irritability, and their impact on motivation, coping, and drinks per day.

Aim 2: Develop the components of an adaptive TMI aimed at reducing postpartum risky drinking. This aim will develop content and decision rules for adaptive tailoring that are consistent with Aim 1 results. TMI components will be based on evidence-based motivational and behavioral interventions for alcohol use and will be adaptively tailored to individual fluctuations in stress, negative mood, and self-efficacy. Components will be refined via iterative cycles of user feedback collected via focus groups with 30 women.

Aim 3: Conduct a pilot micro-randomized trial (MRT) to assess feasibility of design and methods in preparation for a future fully powered optimization trial. We will conduct a pilot MRT with 50 postpartum women with the primary goal of demonstrating feasibility and acceptability of MRT methods and the secondary goal of providing proof-of-concept data on the comparative impact of maternal-focused and drinking-focused messages on proximal (motivation, self-efficacy, and self-regulation) and distal (daily drinking) outcomes.

To achieve these aims, the study will apply the Multiphase Optimization Strategy (MOST) framework. Study activities comprise the Preparation Phase of MOST, and will proceed in three phases to achieve the three study aims. **Phase 1 (Aim 1)** (10 months) will include EMA with 30 women for 14 days aimed at refining the conceptual model and evaluating EMA feasibility. **Phase 2 (Aim 2)** (10 months) will develop TMI components, including message content and decision rules to guide adaptive tailoring of the TMI via an

iterative user-centered design process with 30 women. Phase 3 (Aim 3) (11 months) will consist of a pilot MRT with 50 women to examine feasibility of the MRT design and preliminary effects of the TMI components on the proximal and distal outcomes.

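### The proximal-effect model does not say what each message is compared with under three-option randomization, and it states no maternal-minus-drinking contrast

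*Combined protocol and SAP*

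**What the plan says.** Under TMI Sequence and Randomization, the combined protocol and SAP states: "Upon completion of the decision point EMA, participants will be randomized to one of three options". The options are "1) a maternal-focused message (.40 probability); (2) a drinking-focused message (.40 probability); or (3) no message (.20 probability".

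Aim 3, under Study Purpose and Aims, gives the pilot the "secondary goal of providing proof-of-concept data on the comparative impact of maternal-focused and drinking-focused messages on proximal" and distal outcomes. Purpose of Pilot MRT repeats this goal and says the results will include "preliminary main effects estimates to inform a fully-powered MRT in a future study". Sample and Power adds that "we will interpret results based on effect size rather than statistical significance".

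MRT Data Analysis then gives one model for proximal outcomes: "we will first examine models that include only the intercept and a term for the TMI component". The coefficient is defined as the "mean difference in proximal outcome between person times when the component is delivered and person times when it is not delivered", averaged over the study. Standardized effect sizes are promised for all main effects, and general sources on MRT analysis and on effect sizes are cited. I found no definition of the component, no reference level and no contrast between the two message types. The word *first* implies later models, but none is described.

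**The concern.** A delivered/not-delivered term suits a design with two options. This design has three, so *not delivered* is ambiguous: for the maternal message it may mean the no-message times only, or every time without a maternal message, most of which carry a drinking message. The choice changes what the effect size measures.

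This matters because the effect sizes are to be read on their own, without significance tests, and carried into the planning of the next trial. A reader who sees 0.07 SD for each message cannot tell whether both messages do little against silence, or whether both do three times as much and have been compared largely with each other. The comparison that forms the secondary goal also has no stated estimate.

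**Working it through.** The plan states no effect size, SD or power figure for this analysis, so there is no figure to reproduce. The effect values below are assumptions, in within-person SD units.

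**Inputs from the documents.** 50 women, 28 days, 2 decision points per day, probabilities .40/.40/.20. The maximum is 50 x 28 x 2 = 2,800 decision points (optional nighttime sequence not counted), or 1,120 maternal, 1,120 drinking and 560 none.

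**What each reading estimates.** Let m and d be the maternal and drinking effects versus no message.

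1. One term per message type, fitted to all decision points. The maternal reference is .40/.60 = 2/3 drinking times and .20/.60 = 1/3 no-message times. So bM = m - (2/3)d and bD = d - (2/3)m. Their difference is (5/3)(m - d). Inverting, m = 1.8bM + 1.2bD, d = 1.2bM + 1.8bD and m - d = 0.6(bM - bD).
2. One any-message term: (.40m + .40d)/.80 = (m + d)/2.
3. One term per message type, with no-message times only as reference: m and d.
4. A three-level factor (equivalently, both message indicators in one model): m, d and m - d directly.

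| Assumed m, d | bM (reading 1) | bD (reading 1) | Any message (reading 2) | m - d |
|---|---|---|---|---|
| 0.20, 0.20 | 0.067 | 0.067 | 0.20 | 0 |
| 0.20, 0.30 | 0.00 | 0.167 | 0.25 | -0.10 |
| 0.10, 0.30 | -0.10 | 0.233 | 0.20 | -0.20 |

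On reading 1 a helpful maternal message appears negative whenever m is below (2/3)d. In the second row, subtracting the coefficients gives -0.167 where the true contrast is -0.10. On reading 2, (m, d) = (0.20, 0.00) and (0.10, 0.10) both give 0.10.

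A simulation check (60 trials, 50 women x 56 points, random-intercept mixed model, m = d = 0.30) gave means of 0.099 and 0.106 on reading 1, where the algebra gives 0.10. It gave 0.307 for any message, 0.305 and 0.309 for the three-level factor, and -0.004 for its contrast.

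**Size against sampling error.** The outcome follows only if both the decision-point EMA and the proximal EMA are completed. Participant Incentives uses 80% and 50% as bonus thresholds. If each survey is completed at those rates independently (assumed), usable pairs N are 2,800 x .80 x .80 = 1,792 and 2,800 x .50 x .50 = 700. With independent residuals given the woman and the same effects in all women:

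- message versus rest: SE = sqrt(1/(.4N) + 1/(.6N))
- message versus none: SE = sqrt(1/(.4N) + 1/(.2N))
- maternal minus drinking: SE = sqrt(2/(.4N))

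| Pairs | Versus rest | Versus none | Maternal minus drinking | Shift/SE, d = 0.20 | Shift/SE, d = 0.10 |
|---|---|---|---|---|---|
| 2,800 | 0.0386 | 0.0518 | 0.0423 | 3.5 | 1.7 |
| 1,792 | 0.0482 | 0.0647 | 0.0528 | 2.8 | 1.4 |
| 700 | 0.0772 | 0.1035 | 0.0845 | 1.7 | 0.9 |

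The shift is (2/3)d: 0.133 for d = 0.20 and 0.067 for d = 0.10. It is divided by the versus-rest SE.

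If effects vary between women with SD 0.20 (assumed, independent for m and d), the added variance is .04 x (1 + 4/9)/50 for versus rest, .04/50 for versus none and .08/50 for maternal minus drinking. The versus-rest SEs become 0.0514, 0.0590 and 0.0843, and the d = 0.20 ratios fall to 2.6, 2.3 and 1.6.

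**The case against.** The strongest reply is that the coding is unspecified rather than wrong. MRT Data Analysis speaks of components and models in the plural, which points to one term per message type and makes the any-message reading less likely. That stands, and little weight should rest on the any-message reading, the only one of the four on which the comparison is lost. Nor does the text exclude a no-message reference, which would give m and d undiluted. That stands too: the dilution and possible sign change belong to reading 1 alone.

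Even on reading 1 the coefficient is a valid randomized contrast. A negative value for a helpful message is a correct answer to a different question, and a goal worded as proof-of-concept data might be met by setting two effect sizes side by side. This is right as far as ranking goes. But the sizes are to be interpreted, not only ranked; the gap between the two coefficients is 5/3 of the true one; and the plan gives no instruction to convert them.

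Finally, the plan cites general MRT methods and presents this model as a first step. Those sources were not available here, so I cannot say whether they settle the coding. The documents themselves give no coding for the .40/.40/.20 scheme.

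**Conclusion.** The point holds as a should-fix item. The stated model does not match the three-option randomization, and the contrast that serves the secondary goal is not written down. Fitted literally to all decision points with one term per message type, it reports equal effects at one-third of their size. With the reference restricted to no-message times, or with a three-level factor, there is no dilution, but the text specifies neither.

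A reader might infer that the trial will give biased results or cannot compare the messages. The documents do not support that. Reading 1 keeps the ranking and allows exact recovery, no data are lost, and the remedy uses the same data. Nor are the primary feasibility and acceptability outcomes touched.

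The practical size depends on assumed effects. At d = 0.20 SD the shift is 1.7 to 3.5 standard errors (1.6 to 2.6 with between-woman variation). At d = 0.10 it is 0.9 to 1.7, within sampling noise.

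**What to change.** For each proximal outcome, fit one mixed model with the randomized option as a three-level factor and no message as reference. Report maternal versus none, drinking versus none, and maternal minus drinking, each with a standardized effect size and an interval. Replace the sentence defining the coefficient with these three definitions. If a pooled any-message effect is also wanted, label it as such.

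The cost is SAP wording and slightly more analysis; the design, sample size and type of model stay the same. The message-versus-none standard error exceeds the message-versus-rest one by about 34% if effects are the same in all women (0.0518/0.0386 = 1.34), or by about 15%, 20% and 27% at 2,800, 1,792 and 700 pairs if effects vary between women with SD 0.20. That is the precision of the message-versus-none question itself.

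The 95% half-width for maternal minus drinking (1.96 x SE) is 0.08, 0.10 and 0.17 SD at those numbers of pairs, or 0.11, 0.13 and 0.18 SD with that variation. At low completion the contrast will be imprecise, which is why its interval should be reported.
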